5.1.2 Other study parameters

The following parameters will be recorded for each participant:

- Clinical routine Cardiac MRI parameters (global volumes and function, T1 maps, ventricular fibrosis (LGE))
- Anthropometric data; height, weight
- Clinical information potentially relevant to the study; medical history and medication use

5.2 Study procedures

CMR

We will recruit patients as outlined in paragraph 4.1. Patients will be asked to undergo a cardiac MRI scan protocol at the Amsterdam UMC (Location VUmc) prior to and after surgery. The MRI protocol will be conducted on a 1.5T MRI scanner at the Amsterdam UMC (Location VUmc), with the new 3D whole heart Works In Progress (WIP) package of Siemens. Standard cardiac coils will be used for image acquisition. For triggering, ECG-gating and navigator-gating will be applied.

Intravenous contrast (Gadolinium-based, 0.15mmol/kg) will be administered and total scan time will be approximately 60 minutes.

Abstract outline scan protocol:

1. Localizers
2. LAX cines
3. Contrast administration (Gadolinium)
4. 3D MRA atria/ventricles
5. Flow mitral valve (2D flow)
6. Flow aortic valve (2D flow)
7. 4D Flow scan
8. 3D LGE
9. SAX cines

All scans will be performed using a 1.5 Tesla clinical MRI system (Siemens Sola, Erlangen, Germany) using a 32-channel array coil. The scan protocol included balanced SSFP cine imaging in long axis orientation (two-chamber and four-chamber view). An ECG-gated free-breathing 3D contrast-enhanced MR angiogram (CE-MRA) of the LA and pulmonary veins will be obtained immediately after a 20 mL (1 mL/sec) single dose bolus injection of contrast agent (Dotarem®, Guerbet, Roissy, France) followed by a body weight dependent slow infusion of contrast agent (slow infusion dose; 2.5-30.0 mL, infusion rate; 0.1-0.25 mL/sec) equal to a total dose of 0.4mL/kg. Typical acquisition parameters were: repetition time (TR)/ echo time (TE) 5.5/3.0 ms; flip angle, 25°; in-plane resolution 1.25 × 1.25 mm with slice thickness 2.5 mm (reconstructed to 0.625 × 0.625 × 1.25 mm). Immediately after contrast administration, first 2D flow data at the level of the mitral and aortic valve will be obtained. Then a prospective ECG-gated, 3-dimensional phase-contrast imaging with 3-directional velocity encoding (4D flow CMR) will be performed. Subsequently, high resolution 3D LGE images will be acquired using a navigator-based respiration- and ECG-gated inversion recovery prepared gradient echo pulse sequence applied between 15 and 25

minutes after contrast injection. Voxel size was $1.25 \times 1.25 \times 2.5$ mm (reconstructed to $0.625 \times 0.625 \times 1.25$ mm). Other typical sequence parameters were as follows: TR/TE 5.2/2.4 ms; flip angle, 20° . Finally a stack of short-axis cines will be obtained.

In the occurrence of a clinical relevant incidental finding patients will be informed by their treating physician. During the informed consent patients will be notified of this obligation. Patients who refuse to be informed about clinical relevant incidental MRI findings, will be excluded from this study.

MRI processing

Quantification of LA fibrosis will be performed using commercially available ADAS 3D LA image post-processing software (Galgo Medical, Barcelona, Spain) and open-source CEMRG image post-processing software (King's College London, United Kingdom). The 3D LGE images will undergo stringent quality control (i.e. artefacts, proper myocardial nulling) by two experienced readers prior to post-processing and images will be excluded from analysis if quality is deemed insufficient.

[figure not shown]

Figure 3. Left atrial 3D reconstruction from MRI.

Left Atrial remodeling

LA remodeling will be assessed by quantifying atrial sphericity and calculation of the wall tension calculation using Laplace's law ($T = p \times r / 2T$). This calculation includes pulmonary wedge pressure which is determined using peri-operative Swan-Ganz based pressure measurements during anesthesia, and radius based on atrial volume and wall thickness. Also the relation to quantitative MVI will be determined using 4D-flow MRI processing.

Presence and distribution of LA fibrosis

Quantification of fibrosis surface and the distribution of fibrosis will be assessed using LA 3D reconstructions based on 3D MRA data. Output of this data will be as shown below in Figure 4. The left atrial wall is segmented for accurate geometric localization of fibrosis (*Figure 4A*) and the severity of fibrosis will be shown as quantified surface area (*Figure 4B*).

[figure not shown]

Figure 4. Left atrial segmentation (A) for accurate assessment of geometric distribution of fibrosis and severity of fibrosis shown as quantified surface (B).

4D Flow

4D-flow data will be corrected for Maxwell terms in the image reconstruction at the scanner, and velocity aliasing during post-processing. 4D flow data will be co-registered with the cine images to guide left atrial anatomic orientation. Mean and peak flow velocity data will be derived using dedicated research software (MASS version 2017-Exp, Leiden University Medical Center, Leiden, the Netherlands). Furthermore, the volume fraction in the left atrium with a flow velocity below 10cm/s during the entire cardiac cycle will be determined.

Blood samples

Blood samples will be collected two weeks before and 3 months after surgery to assess biomarkers associated with atrial structural remodeling and/or fibrosis (NT-proBNP, TNF- β , Angiotensin II, cytokines).

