4.2 Inclusion criteria

The following patients will be targeted for inclusion.

- Patients that meet the criteria for elective mitral valve repair surgery according to the European clinical guidelines (class I recommendation);
 - Symptomatic, chronic severe mitral valve insufficiency due to degenerative valve disease with a left ventricular ejection fraction (LVEF) >30%.
 - Asymptomatic, chronic severe mitral valve insufficiency due to degenerative valve disease with a LVEF <60% and/or a left ventricular end-systolic diameter (LVESD) >45 mm.

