4.3 Exclusion criteria

Patients that will be excluded from our study are patients;

- not able to provide written informed consent.
- under the age of 18.
- with a history of cardiac surgery
- with AF
- with any comorbidity besides MVI.
- with claustrophobia or any other contra-indication for MRI
 - Each participant will be requested to fill out the “Questionnaire for MRI research with human volunteers” (“*Vragenlijst voor MRI-onderzoek bij testpersonen*”). This standard MRI safety document that is required to be filled in by anybody undergoing MRI scanning contains (among other items) questions on whether

or not the participant has ever had any surgical procedures, has any (metallic) implants or has any other metallic parts in his/her body e.g. splinters.

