8.3 Benefits and risks assessment, group relatedness

This is an MRI study with use of contrast media (Gadolinium). Gadolinium-based contrast enhanced imaging is considered the clinical gold standard for identifying cardiac fibrosis in both the ventricles and atria. [10, 11] Unfortunately, reliable assessment of atrial fibrosis without use of a contrast agent is currently not feasible.

Although rarely reported in previous literature, nephrogenic systemic fibrosis (NSF) is a more common side effect associated with gadolinium than brain damage. In addition, NSF was more commonly associated with contrast agents with a linear molecular structure. However, in this study we will use the contrast agent gadoterate meglumine (Dotarem®). This is a macrocyclic contrast agent with great stability and low risk profile. [12] This favorable profile was recently reconfirmed. In a large cohort, it was demonstrated that gadoterate meglumine is a safe contrast agent. In only 70 (0.12%) out of 35.499 patients who underwent contrast enhanced MRI with gadoterate meglumine, a transient adverse event occurred (urticaria 0.03%, nausea 0.02%, vomiting 0.01%, respectively). In none of the patients NSF was observed. [13] Based on these reports, we believe it is safe and justifiable to use gadoterate meglumine for this study at a dose recommended in the literature.

The use of the contrast agent and potential side effects associated with administration, including transient cold/burning sensation, urticaria, nausea and vomiting will be described in the information letter.

There are no direct benefits for individuals participating to our study.

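### The fixed 20 mL contrast bolus in section 5.2 already exceeds the stated total of 0.4 mL/kg for any patient under 50 kg, and eligibility sets no weight limit

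*Combined protocol and SAP*

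**What the plan says.** Section 5.2 (Study procedures, CMR) sets out contrast administration in three parts:

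- a fixed bolus, with the angiogram obtained "immediately after a 20 mL (1 mL/sec) single dose bolus injection of contrast agent";
- a slow infusion that varies with body weight, described as "slow infusion dose; 2.5-30.0 mL, infusion rate; 0.1-0.25 mL/sec";
- a combined amount "equal to a total dose of 0.4mL/kg".

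Earlier in the same section the dose also appears by amount of substance: "Intravenous contrast (Gadolinium-based, 0.15mmol/kg) will be administered".

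Section 4.2 defines eligibility by surgical indication, ejection fraction and ventricular diameter. Section 4.3 excludes patients "under the age of 18" and adds clinical and MRI-related exclusions. Neither names a minimum or maximum weight. Section 5.1.2 lists weight only as something to be recorded. Section 8.3 defends the agent's safety on the ground that the study will "use gadoterate meglumine for this study at a dose recommended in the literature", without giving a figure, so 5.2 is the only place where the dose is set.

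**The concern.** A total proportional to weight cannot be built from a constant plus a non-negative remainder at every weight. Once the constant exceeds the total, the remainder would have to be negative. The bolus is given first and 5.2 contains no provision for reducing it. For a light enough patient, staff must either depart from the stated bolus or exceed the stated total, and the text does not say which.

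What is at stake is the coherence of a dosing instruction. At low weight any deviation is upward, and it would occur twice, because the same scan is scheduled before and after surgery. The safety argument in 8.3 refers to a recommended dose, and 5.2 is where a reader would look for it.

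**Working it through.** **Inputs, all from section 5.2.** Bolus B = 20 mL, fixed. Total D = 0.4 mL/kg. Infusion range 2.5 to 30.0 mL.

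**Reproducing the plan's figure.** For weight w, the infusion needed is D × w − B. At 80 kg this is 0.4 × 80 − 20 = 12 mL, and (20 + 12)/80 = 0.4 mL/kg, as stated. The printed infusion range corresponds to (20 + 2.5)/0.4 = 56.25 kg up to (20 + 30)/0.4 = 125 kg. Within that span the rule delivers its total.

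**Alternative reading.** If 0.4 mL/kg applied to the infusion alone, 2.5 to 30.0 mL would correspond to 2.5/0.4 = 6.25 kg up to 30/0.4 = 75 kg. That does not fit an adult study, and the text calls the figure a total, so this reading is set aside.

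**Where the rule fails.** The bolus alone equals the total when w = B/D = 20/0.4 = 50 kg. Below that weight:

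| Weight (kg) | Total 0.4 × w (mL) | Infusion needed (mL) | Bolus alone (mL/kg) | Bolus over total |
|---|---|---|---|---|
| 50 | 20.0 | 0.0 | 0.400 | 0% |
| 49 | 19.6 | −0.4 | 0.408 | 2.0% |
| 48 | 19.2 | −0.8 | 0.417 | 4.2% |
| 45 | 18.0 | −2.0 | 0.444 | 11.1% |
| 40 | 16.0 | −4.0 | 0.500 | 25.0% |

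These results use only the bolus and the total, not the infusion range.

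**If the infusion range is binding.** Should 2.5 mL be a mandatory minimum, at least 22.5 mL is given and the total is exceeded below 56.25 kg: 22.5/50 = 0.45 mL/kg at 50 kg (12.5% over) and 22.5/45 = 0.50 mL/kg at 45 kg (25% over). Should 30 mL be a hard maximum, the total falls short above 125 kg. The paragraph does not settle this. It also uses descriptive wording such as "Typical acquisition parameters were", which makes a typical range plausible.

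**The two dose forms.** 0.15 mmol/kg equals 0.4 mL/kg only at 0.15/0.4 = 0.375 mmol/mL. No concentration is stated, so a conflict is possible but the documents do not show one. The 50 kg result does not depend on it.

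**The case against.** The best defence is that the sentence already names its target. The weight-based total governs, the infusion is the remainder, and all that is missing is a clause for the lightest patients. If the infusion range is only descriptive, the rule works at every weight from 50 kg up. The study enrols 20 adults at one centre, possibly none of them under 50 kg, and the excess at 48 kg is 0.8 mL. A patient of stable weight would receive the same volume at both scans, which limits any effect on the before-and-after comparison. Nothing in the documents calls for a weight criterion, so its absence is not an eligibility defect.

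Most of this stands as an argument about importance. It supports a low rating, and it is fair to keep the 12.5% and 25% figures out of the headline because they depend on an uncertain reading. It does not make the rule consistent. The bolus is stated as a fixed volume given before the infusion, no text permits reducing it, and no other section covers patients under 50 kg. The absence of a weight limit matters only because it leaves those patients eligible.

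**Conclusion.** The concern holds, as a minor point. Below 50 kg, the rule in 5.2 exceeds its own stated total before any infusion starts, by 4.2% at 48 kg and 11.1% at 45 kg. This follows from two figures in the same sentence and needs no outside assumption. The larger excesses, and the 56.25 kg and 125 kg limits as points of failure, apply only if the infusion range is binding.

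How many patients are affected is unknown and may be none. No safety threshold is said to be crossed, and no endpoint, sample size or analysis is touched.

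**What to change.** In 5.2, replace the fixed bolus with a capped one:

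- bolus = the smaller of 20 mL and 0.4 mL/kg × weight;
- infusion = 0.4 mL/kg × weight − 20 mL, or 0 mL if that is negative.

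This gives 18 + 0 mL at 45 kg, 20 + 0 mL at 50 kg, 20 + 2 mL at 55 kg and 20 + 12 mL at 80 kg. Label the 2.5 to 30.0 mL range as typical, or replace it with an explicit maximum dose. While editing the section, the sponsor could also name one governing dose and give the product concentration, so that the mmol/kg and mL/kg forms can be converted. Which dose is right is for the sponsor to decide.

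The cost is one or two sentences. Visits, sample size and analysis do not change, and no weight criterion is needed.

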post-processing techniques prior to and after mitral valve repair surgery to gain insight on the clinical role and predictive value of atrial fibrosis in this patient population.

In addition, we aim to assess the effects of (reduced) volume overload on atrial wall texture, geometry and function.

It is hypothesized that the atrial fibrosis surface area paradoxically will increase after mitral valve surgery because of global shrinkage of the LA caused by the reversed remodeling process.[1] As a consequence, more frequently atrial fibrosis related events including (paroxysmal) AF, may be observed in these patients.

With this insight, CMR can become clinical valuable for the indication and timing of surgical intervention in these patients. Surgical therapy might be renounced for example when a substantial increase of fibrosis surface is expected post-surgically causing a higher risk for AF, HF, PH and a reduced quality of life. On the contrary, surgical therapy might be considered in an earlier stage of disease when the amount of fibrosis is still limited regarding its expected post-surgical development.

[figure not shown]

Figure 1. Pathway to structural LA remodeling caused by a pathological trigger.

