5. METHODS

5.1 Study parameters/endpoints

5.1.1 Main study parameter/endpoint

The main study parameters are:

1. Severity of MVI prior to and after surgery (defined as regurgitation volume in ml)
2. Left atrial remodelling prior to and after surgery
 - Left atrial volume
 - Calculated left atrial sphericity
 - Estimated wall tension (wall thickness, radius, pulmonary wedge pressure)
 - Mitral regurgitation flow measurement (quantitative)
3. Presence and distribution patterns of LA fibrosis
 - Quantification of fibrosis surface (severity)
 - Geometric distribution of fibrosis (localization)
4. Blood flow patterns in the LA (4D Flow)
 - Flow velocity (mean and peak)
 - Static fraction
 - Kinetic energy

Secondary study parameters/endpoints -Fibrosis associated biomarkers derived from blood samples (NT-proBNP, TNF- β , Angiotensin II, cytokines)

-Heart failure symptoms monitoring derived from questionnaire preoperative and at postoperative follow-up

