7. STATISTICAL ANALYSIS

7.1 Primary study parameters

CMR qualitative and quantitative analyses will be performed on a dedicated work-station with counseling of investigators experienced in the post-processing of CMR techniques.

The included data will be presented as mean \pm standard deviation. Ratios will be given for statistical assessment of non-continuous variables. Correlation analyses will be used to analyze differences between continuous parameters. Confidence intervals (95%) will be used and a $p < 0.05$ will be considered statistically significant. Fisher exact test will be performed to verify significance, risk ratio (RR) and 95% confidence intervals. SPSS 26.0 (SPSS Inc, Chicago, IL) for Windows is used to assess statistical analyses.

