9. ADMINISTRATIVE ASPECTS, MONITORING AND PUBLICATION

9.1 Handling and storage of data and documents

The participant's identity will remain confidential. His or her name will not be published and will not be disclosed to anyone outside the research group. All personal details and other identifiable data provided or collected during this study will be kept in the strictest confidence. Participants will be assigned a code number following their first contact with the researcher. This number will be used throughout the project and will be the only identifier on physiological archival data and MRI data. No identifiable (e.g. name etc.) of participants will be revealed at scientific meetings, conferences, presentations, publications or any other vehicles of public communication. In any such publication arising from this research the individual results will not be identifiable. Only the research team will have access to the collected data.

- Each researcher will store documents bearing identifiable and personal information in a locked cabinet with access strictly restricted to members of the research group.
- All computerised data/information will be stored on pass-word protected computers, to which only a member of the research team has access.
- Code numbers will be used for all computerised data/information collected. These data are therefore stored in a coded fashion.
- All gathered data/information will be stored for the duration of the study. It will then be kept in a locked cabinet for up to 15 years

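### Section 5.2 specifies no masking and no reading order for LGE quality decisions or LA fibrosis quantification, although the protocol expects fibrosis to increase after surgery

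*Combined protocol and SAP*

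**What the plan says.** **Quality decision.** Section 5.2 (MRI processing) names artefacts and correct myocardial nulling as the criteria for the 3D LGE images. The check is made "by two experienced readers prior to post-processing and images will be excluded from analysis if quality is deemed insufficient". No numeric threshold is given, and there is no rule for disagreement between the two readers.

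**Quantification.** The same section states: "Quantification of LA fibrosis will be performed using commercially available ADAS 3D LA image post-processing software", together with a second, open-source package. The atrial wall is segmented on a reconstruction from the MRA data, and fibrosis is reported as a surface area. The section gives no enhancement threshold and does not say who operates the software. Section 7.1 adds only that analyses are done "with counseling of investigators experienced in the post-processing of CMR techniques".

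**Expected direction.** Section 1 states: "It is hypothesized that the atrial fibrosis surface area paradoxically will increase after mitral valve surgery because of global shrinkage of the LA". The Summary says the same.

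**Role of fibrosis.** Section 5.1.1 lists four groups of main parameters. Fibrosis surface and its localisation form the third.

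**Coding.** Section 9.1 gives each participant one code number for confidentiality: "This number will be used throughout the project and will be the only identifier on physiological archival data and MRI data".

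No section mentions blinding, masking, reading order, independent reading or adjudication.

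**The concern.** The fibrosis value depends on two steps: deciding which images are good enough to use, and segmenting and quantifying the wall. The first is explicitly a judgement. For the second, the plan does not say how much operator input is allowed. If a reader knows that a scan is post-operative, or that it comes from a control, the stated expectation can affect either step.

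The main fibrosis comparison is within patients, before against after surgery. A small shift that always goes the same way does not average out over patients: it adds directly to the mean change and is indistinguishable from a real increase. Section 1 says that findings of this kind might lead to surgery being withheld or brought forward, so the direction and size of the estimate matter even in a pilot.

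**Working it through.** **1. Is there any masking in the plan?** I read Sections 3, 4, 5.2, 7 and 9.1 for anything that would conceal time point or group.
- Section 5.2: two readers, two named criteria and the sequence (quality check, then post-processing). No concealment and no reading order.
- Section 7.1: experienced guidance for the analysis. This concerns expertise, not independence or masking.
- Section 9.1: one code per participant, used throughout. Both scans of a patient therefore carry the same code. It hides identity but neither masks the time point nor prevents the two scans being read together.
- Sections 3 and 4.1: controls come from an existing database. Nothing describes mixing their scans with those of patients.

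**2. How much could a reader shift matter?** The plan has no power or sample-size figure to reproduce; Section 4.4 gives 20 patients as a pilot number. What follows is an illustration.

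Inputs from the plan: n = 20 patients scanned twice (Sections 3 and 4.4); significance at p < 0.05 (Section 7.1).

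Assumptions: a two-sided paired t-test (Section 7.1 names no paired test), 20 complete pairs, a true mean change of zero, and a constant reader shift b in units of the SD of the paired changes. The documents give neither an SD nor a reader-error figure, so a range of b is shown.

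With 19 degrees of freedom the critical value is 2.093, so an observed mean change of 2.093/√20 = 0.47 SD is enough for significance. Under a shift b the test statistic is noncentral t with noncentrality b√20.

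| Shift b | b√20 | Any significant result | Significant increase |
|---|---|---|---|
| 0 | 0 | 5.0% | 2.5% |
| 0.10 | 0.447 | 7.1% | 6.2% |
| 0.25 | 1.118 | 18.6% | 18.5% |
| 0.30 | 1.342 | 24.7% | 24.6% |

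From 0.25 SD upwards, almost every false positive lies in the hypothesised direction.

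**3. Fewer usable pairs.** Section 5.2 allows images to be excluded, and Section 5.4 deletes the data of withdrawn subjects. If 4 pairs were lost independently of their result (an assumption), then n = 16 and the noncentrality is b√16 = 4b. The two-sided rates become 6.6%, 15.5% and 20.3% at 0.10, 0.25 and 0.30 SD: somewhat lower, with the same pattern.

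**4. Patients against controls.** Assume an unpaired t-test of 20 against 10 and a reader bias of 0.25 SD of the individual values. The noncentrality is 0.25/√(1/20 + 1/10) = 0.645 and the two-sided rate is 9.6%. At 0.5 SD it is 23.9%. The plan specifies no test for this comparison, so these figures are also only illustrative.

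**The case against.** **Silence is not unmasked reading.** A reader might infer that the scans will be read unmasked and side by side. The documents do not say so; they say nothing either way. This stands, and the point is limited to the absence of a specified safeguard. An unspecified safeguard cannot be relied on or audited.

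**Quality control already comes first.** It might also be inferred that readers could reject scans because the fibrosis result is unwelcome. Section 5.2 does not support that: rejection precedes post-processing, uses two readers and has named criteria, so no computed fibrosis value exists at that stage. What remains is narrower. The readers see the LGE image itself and may know the time point when they judge it.

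**Software standardises the measurement.** Partly fair. How far an operator can move the value is not described, so subjectivity is not shown. But the plan fixes no enhancement threshold and sets no limit on operator input, so it gives no basis for ruling it out. The guidance mentioned in Section 7.1 is not evidence of bias.

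**Masking will leak.** This stands for both comparisons. Surgical changes may show on the second scan. The expected shrinkage of the atrium may hint at time point, and dilated atria in severe mitral insufficiency may hint at group. Masking would still remove the label and the deliberate paired reading, and the leakage can be recorded.

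**It is a pilot with several main parameters.** Also fair. A reader might conclude that the study's whole result is at risk. The concern reaches only the fibrosis parameters, one of four groups, and the plan makes no power claim. Section 7.1 nevertheless applies p < 0.05, and a pilot's fibrosis estimate is of little use if it may reflect expectation.

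**Conclusion.** The concern holds as a gap in the design. The protocol states an expected direction for fibrosis but specifies neither masking nor reading order for the quality decision and the quantification. Reader expectation could therefore bias the fibrosis comparison.

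The documents do not allow the bias to be sized. The rates of about 7%, 19% and 25% rest on an assumed test, an assumed constant shift, complete pairs and no true change; they would apply to any study of 20 pairs. At the low end the effect is minor, and at a quarter of an SD it is not. The documents do not show that bias will occur or that it would produce the expected increase. This is a worthwhile low-cost improvement, to be settled before images are read, because masked reading by the same readers cannot be restored afterwards.

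**What to change.** Add to Section 5.2:

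- Every LGE/MRA set (pre-operative, post-operative and control) receives its own random code, with scan date, time point and group removed. The participant code of Section 9.1 is not shown to readers.
- The same readers check quality and quantify fibrosis in random order, not in patient pairs.
- Quality decisions are recorded and locked before quantification. Section 5.2 already has this sequence; the formal lock is new.
- The key is released only after all fibrosis values are locked.
- Exclusions are reported by time point and group.
- Readers record when they believe they recognise the time point or group.
- Review for clinically relevant incidental findings (Sections 5.2 and 6.4) is kept outside the masked research reading, or unmasking is allowed for it, so that reporting to patients is not delayed.

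The cost is small: the same readers, software and scans, plus recoding and a shuffled work list for at most 20 × 2 + 10 = 50 image sets. The downsides are that batch reading delays results and that masking will be incomplete, because surgical changes and atrial size may reveal time point or group. The report should say so.

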2. OBJECTIVES

Primary Objective:

To assess

- the effects of (reduced) volume overload on the left atrial wall texture (presence, amount and location of atrial fibrosis) and associated geometry and function in patients with MVI, prior to and after elective mitral valve repair surgery.

Secondary Objectives:

To assess;

- the value of LA fibrosis in stratification and timing of mitral valve repair surgery.
- the impact of atrial fibrosis on myocyte contractile function (atrial strain, quantified by CMR).
- whether left ventricular (LV) volume overload results in increased extra cellular volume (ECV) and whether this is reversible after mitral valve repair surgery.
- the impact of LA remodeling on right atrial (RA) function and tissue characteristics.
- the predictive value of LA fibrosis for outcomes of AF and atrial function during post-surgical follow up

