4.4 Sample size calculation

This study is designed as a pilot study, since we are the first to assess the effect of LA fibrosis and its characteristics prior to and after mitral valve repair surgery.

Therefore we aim to include;

- 20 patients with MVI which are admitted to mitral valve repair surgery

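### LGE scans are excluded image by image with no paired analysis defined, so the before and after LA fibrosis summaries can come from different patients

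*Combined protocol and SAP*

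**What the plan says.** All references are to the combined protocol and SAP.

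- **Objective (section 2).** Fibrosis, geometry and function are to be assessed "prior to and after elective mitral valve repair surgery", that is, in the same patients at two times. The second scan is at three months (section 3).
- **Quality control (section 5.2, MRI processing).** The 3D LGE scans are checked "by two experienced readers prior to post-processing", and "images will be excluded from analysis if quality is deemed insufficient". The section gives no rule for the patient's other scan, for a repeat scan or for reader disagreement. It does not say whether the readers are blinded to time point.
- **Analysis (section 7.1).** "The included data will be presented as mean" with standard deviation, and differences between continuous parameters are to be examined by correlation. There is no change score, paired test, paired analysis set or method for missing scans.
- **Size (section 4.4).** The target is "20 patients with MVI which are admitted to mitral valve repair surgery", with no allowance for unusable scans.
- **Withdrawal (section 5.4).** Data of withdrawn subjects are deleted. This does not cover a patient who stays in the study but has one failed image.

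**The concern.** A before/after question needs the same patients on both sides. If one scan of a pair is dropped and the other kept, the two means rest on overlapping but different groups, and their difference mixes change within patients with differences between patients.

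With random failure, the stake is precision. If failure is related to fibrosis, the difference can also be biased. The protocol gives some reason to ask. AF is an exclusion criterion at entry (section 4.3), whereas after surgery the introduction expects that "more frequently atrial fibrosis related events including (paroxysmal) AF, may be observed in these patients". The LGE scan is a "navigator-based respiration- and ECG-gated inversion recovery prepared gradient echo pulse sequence". That an irregular rhythm would spoil such a scan is a technical assumption and is not stated in the documents. If it is true, losses would fall mainly on the second scan.

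**Working it through.** **1. Figure to reproduce.** The 20 patients are a pilot number with no effect size, SD or power behind them, so there is no calculation to reproduce.

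**2. How often the two groups would differ.** Input from the plan: N = 20 (section 4.4). Assumption: each scan fails independently with probability f. The documents give no f, so a range of 5% to 30% is shown.

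- Expected pairs = 20(1−f)²
- Expected patients with exactly one usable scan = 20 × 2f(1−f)
- Chance of at least one such patient = 1 − [1 − 2f(1−f)]²⁰

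For f = 5%: 2 × 0.05 × 0.95 = 0.095, and 1 − 0.905²⁰ = 0.86. For f = 10%: 2 × 0.10 × 0.90 = 0.18, and 1 − 0.82²⁰ = 0.98.

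| f (assumed) | Expected pairs | Expected one-scan patients | Chance of at least one |
|---|---|---|---|
| 5% | 18.1 | 1.9 | 86% |
| 10% | 16.2 | 3.6 | 98% |
| 20% | 12.8 | 6.4 | >99% |
| 30% | 9.8 | 8.4 | >99% |

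**3. Precision when failure is random.** Take between-patient SD 1, correlation ρ = 0.8, 20 first scans and 16 second scans (20% lost).

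- Separate means: SE = √(1/16 + 1/20 − 2 × 0.8/20) = √0.0325 = 0.18
- Complete pairs: SE = √(2 × (1 − 0.8)/16) = √0.025 = 0.16

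The variance gap is (1/16 − 1/20)(2ρ − 1). In this setting separate means are therefore less precise than pairs whenever ρ exceeds 0.5. Either way some precision is lost against 20 full pairs. The 95% CI half-width for the mean paired change is 0.47 SD of the change with 20 pairs, 0.53 with 16 and 0.60 with 13.

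**4. Bias when failure is related to fibrosis.** Simulation with no true change; every input is assumed. In the milder setting ρ is 0.5 or 0.8, and 10% to 30% of second scans fail, with failure odds doubling per SD of the driver. First scans fail at random at the same rate. Bias is in between-patient SDs.

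| Failure of second scan driven by | Separate means | Complete pairs |
|---|---|---|
| Nothing (random) | 0.00 | 0.00 |
| Baseline fibrosis | −0.03 to −0.15 | +0.01 to +0.10 |
| Follow-up fibrosis | −0.07 to −0.19 | −0.01 to −0.09 |
| The change | −0.02 to −0.09 | −0.04 to −0.19 |

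If failure depends equally on the current fibrosis level at both visits and the distribution does not shift, both columns are 0.00.

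In a stronger setting ρ is 0.6 to 0.8, only second scans fail (20% to 30%), and the odds rise 2.7- to 7.4-fold per SD. Here a likelihood-based model using all evaluable scans is added.

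| Driver | Complete pairs | Likelihood model |
|---|---|---|
| Baseline fibrosis | +0.03 to +0.15 | 0.00 |
| Follow-up fibrosis | −0.03 to −0.15 | −0.07 to −0.27 |
| The change | −0.11 to −0.34 | −0.10 to −0.29 |

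In this setting separate means are biased by −0.10 to −0.30 (baseline driver) and −0.17 to −0.37 (follow-up driver). For scale, the CI half-width with 20 full pairs is t₁₉ × √(2(1−ρ)/20), which is 0.42 at ρ = 0.6 and 0.30 at ρ = 0.8.

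**The case against.** **Section 7.1 describes; it does not compare.** It says how data will be presented and never states that two separate means will be contrasted. That is fair. But it offers no other estimate of the before/after difference in fibrosis, so separate summaries are what a reader following the plan would produce.

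**Quality is judged before fibrosis is quantified, on artefacts and nulling.** This limits exclusion driven by the result. It does not help if something related to fibrosis, such as rhythm, affects image quality itself.

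**This is a 20-patient pilot, and the rule covers only LGE.** Both are true. Fibrosis is one of four groups of main parameters in section 5.1.1; volume, sphericity and flow are not subject to this rule. The point is limited accordingly.

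**Two stronger readings are tempting, and the documents support neither.**

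- A reader might infer that patients with both scans are a selected group and that the result is biased towards the hypothesised increase. The documents give no failure rate and no link between image quality and fibrosis. Upward bias in pairs arises when failure follows baseline fibrosis. The introduction's own reasoning runs from increased fibrosis area after surgery to AF. That is closer to failure driven by follow-up fibrosis or by the change, and there the bias is downward, against the hypothesis.
- A reader might infer that a mixed model removes the problem and should be the main analysis. Its zero bias holds only if loss depends on observed values. If loss follows unseen follow-up fibrosis, it is more biased than complete pairs. Even under baseline-driven loss at the strongest setting (30% failing, 7.4-fold odds), with n = 20 its root mean squared error is 0.267 against 0.275 for pairs at ρ = 0.6, and 0.196 against 0.186 at ρ = 0.8. It is a trade-off, not a clear gain.

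**Conclusion.** The point holds as a gap in the plan. Exclusion is per image, no within-patient change or paired set is defined, and the two fibrosis summaries can therefore rest on different patients. Even an assumed 5% failure per scan makes this likely (86%), and 10% makes it nearly certain (98%), provided that failures are independent.

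If failure is random, the consequence is loss of precision only. Bias is possible if failure relates to fibrosis, but it is not shown, and its size rests wholly on assumed inputs. Within complete pairs it is positive if baseline fibrosis drives failure and negative if follow-up fibrosis or the change does. A paired analysis cures the mismatch of patients under any mechanism; it does not cure selection, and when the change itself drives failure its bias exceeds that of separate means. This is why reporting the exclusions matters as much as the choice of estimate.

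**What to change.** In sections 5.2 and 7.1:

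1. Define the fibrosis change within patients. Name patients with two evaluable LGE scans as the main set, and report the mean paired difference with its 95% CI. State that separate before and after means will not be compared.
2. Add, as a sensitivity analysis, a mixed model for repeated measures (time as a factor, unstructured 2×2 covariance) using every evaluable scan. State that it assumes loss depends only on observed values.
3. Report the number of excluded images at each visit with reasons, and the baseline fibrosis of patients with and without an evaluable second scan.

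The cost is a few sentences, one extra model and one table. The downside is that patients with a single usable scan do not contribute to the main estimate, although they do enter the sensitivity analysis.
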